9.2. Adverse Events

eCRF form: “ADVERSE EVENTS”.

All registered AEs will be coded using the MedDRA version 22.0 (or a later version if available).

Treatment-emergent AEs will be summarized by the overall incidence of at least one event, incidence by body system, and incidence by body system and preferred term. Each subject will contribute only once (e.g., the first occurrence) to each of the rates, regardless of the number of occurrences (events) the subject experiences. Treatment-emergent AEs will be summarized by

**MC2-01-C6_STATISTICAL ANALYSIS PLAN_Final 3.0_07 September 2020**

severity (mild, moderate, or severe), and by relationship to trial product (none, possible, probable, or definite). An AE is treatment-emergent if its date of onset is on or after the date of the first application of the IP.

Only treatment emergent AEs will be summarized. In the listings, however, all occurrences of the AEs will be presented.

Number (percentage) of subjects and number of AEs will be presented for the Safety population in the following tables:

- All treatment-emergent AE / SAE;
- Treatment-emergent AE / SAE related to the study drug (relationship to trial product assessed by the investigator as possible, probable, or definite including those events where assessment is missing);
- TEAE by maximum severity;
- TEAE by closest relationship to study drug;
- TEAE related to study drug by maximum severity;
- TEAE related to cosyntropin;
- TEAE related to study procedures;
- TEAE leading to the permanent discontinuation of study drug (Action taken with IP=“Drug withdrawn”);
- TEAE leading to withdrawal (Did subject withdraw due to this AE? = “Yes”);
- TEAE leading to death (Outcome = “Death”);
- Non-serious TEAEs that occurred at a frequency of $\geq 5\%$ (if no events occurred at the 5% threshold all non-serious TEAEs will be tabulated).

This set of tables will be repeated for the adverse events occurring up to Visit 3 / Week 4. Treatment-emergent adverse events with start dates on or prior to Visit 3 / Week 4 date will be summarized separately. If subject discontinued from the study prior to Visit 3 / Week 4 his/her adverse events will also be included in these summaries. If subject missed Visit 3 / Week 4 the planned date of visit (study day) will be used to subset the events occurring up to Week 4.

Tables of TEAEs by maximum severity (closest relationship to study drug) will be prepared using the following rules: each SOC / PT category will include only the AEs with the worst severity (closest relationship) for each subject. In the Overall category, all AEs of the subjects will be presented. Each subject will be counted only once with the worst severity (closest relationship) in each SOC and each PT level as well as in the Overall level.

In case if severity or relationship to study drug is missing, the worst case value will be assumed and used in the summary.

All AEs/SAEs will be listed. Non-treatment emergent adverse events will be identified accordingly in the listing. Discontinuations from the trial due to AEs and SAEs will be listed by subject.

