7.6.2 HPA axis suppression/ ACTH challenge test

Adrenal function will be assessed in a challenge test with an intravenous dose of ACTH (cosyntropin). Measurement of serum cortisol levels pre- and post- stimulation with cosyntropin 0.25 mg is the accepted standard method used to evaluate adrenal suppression. The ACTH challenge test will be performed at SV2, Week 4 and Week 8 visits. The test consists of blood sampling starting between 7 and 9 am. Following the blood sample, an intravenous bolus injection of 0.25 mg cosyntropin is given at time zero ($t=0$ minutes). Serum cortisol concentration at $t=30$ minutes will reflect stimulation of the adrenal glands induced by cosyntropin.

The following criterion will define an adrenal suppression:

- the 30-minute post-stimulation level below 18 $\mu\text{g}/\text{dL}$ (500 nmol/l).

Week 4: If HPA axis suppression is noted at Week 4, the application with the MC2-01 cream should be discontinued. The subject should continue in the trial and the ACTH challenge test is repeated at the Week 8 visit. If HPA axis suppression is noted at Week 8, the ACTH challenge test has to be repeated at a follow-up visit 28 days (\pm 2 days) after the Week 8 visit (see [Section 7.12](#)).

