- a) A washout period of up to 6 weeks must be completed if the subject has been treated with anti-psoriatic treatments or other relevant medication, as defined by exclusion criteria.

There should be at least four days between SV1 and SV2 in order to keep the food diary for 4 days prior to SV2. Items denoted in [brackets] must be reviewed during screening, to assess if the subject is otherwise eligible. Such items must be checked for any change in eligibility status at Visit 1/Day 0 after the washout is completed.

- b) Follow-up visit is required 2 weeks after the Week 8 visit. For subject with HPA axis suppression at Week 8 the follow-up visit should be 4 weeks after the Week 8 visit.

If the albumin-corrected serum calcium or the urinary calcium creatinine ratio is elevated at Week 8 a repeat test should be performed. In case of a repeat of the urinary calcium creatinine ratio the subject should be instructed to record the calcium intact 4 days prior to the visit.

For Czech Republic and Hungary: if an on-site visit is not required the follow up visit can be a telephone call 2 weeks after Week 8 to ask for the wellbeing of the subject.

In addition, subjects discontinued due to a treatment-related AE will be monitored until the AE is resolved or until the medical condition of the subject is stable.

- c) Written informed assent must be provided by the subject and written informed consent must be provided by the parent(s), legal guardian(s) and the consent documents signed by the investigator or designee before any trial related procedures are carried out. For subjects requiring a washout period, informed assent/informed consent must be completed prior to washout.
- d) All female subjects.
- e) If serum albumin-corrected serum calcium is above the reference range at Week 4 a repeat test should be performed at Week 6.
- f) The ACTH challenge test must be performed between 7 and 9 AM, before IP application.
- g) If the urinary calcium: creatinine ratio is above the reference range at Week 4, a repeat test should be performed, and the food diary filled in at Week 6. If the repeat test is also above the reference range, 24-hour urine collection must be performed.
- h) Blood samples for PK analysis are drawn before IP application (pre-dose sample) and 1, 3, and 5 hours after IP application.
- i) AEs are to be collected from the date of signing informed assent/informed consent and first trial-related activity is performed.

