**MC2-01-C6_STATISTICAL ANALYSIS PLAN_Final 3.0_07 September 2020**

result will be listed.

For quantitative measurements, changes from baseline will be calculated as [value at post-baseline visit X – baseline value].

The baseline value for a variable in common cases is defined as the last non-missing value collected before the first study drug application.

Study day for each event will be calculated from the reference start date (date when subject was first exposed to study drug).

If the date of the event is on or after the reference date, then

$$\text{study day} = (\text{date of event} - \text{reference date}) + 1.$$

If the date of the event is prior to the reference date, then

$$\text{study day} = (\text{date of event} - \text{reference date}).$$

For partial dates study day will not be calculated.

The following visit windows were defined in the clinical study protocol:

| Visit Name | Visit Short Name | Anchor | Target Day | First day of the visit window | Last day of the visit window |
|-------------------|------------------|-------------------|------------|-------------------------------|------------------------------|
| Screening Visit 1 | SV1 | First application | - | -42 | -8 |
| Screening Visit 2 | SV2 | First application | - | -7 | -4 |
| Visit 1 (Day 0) | V1 (Day 0) | First application | 1 | 1 | 1 |
| Visit 2 / Week 2 | V2/Week 2 | First application | 15 | 13 | 17 |
| Visit 3 / Week 4 | V3/Week 4 | First application | 29 | 27 | 31 |
| Visit 4 / Week 6 | V4/Week 6 | First application | 43 | 41 | 45 |
| Visit 5 / Week 8 | V5/Week 8 | First application | 57 | 55 | 59 |
| Follow-up Visit | FU | Last application | 15 | 13 | 17 |

Assessments performed out of the planned visit windows will be assigned to the nearest of the surrounding planned visits if there is no valid result from a planned assessment for this visit. If assessments at both surrounding visits are missing and they are equidistant, the assignment is performed to the later one. Otherwise the assessments will not be included in summaries and will be listed only.

Unscheduled and early termination visit assessment can be assigned to the planned visit in a similar manner. Unscheduled assessment can also be used in the derivations such as baseline or most extreme post-baseline assessments. All assessments including unscheduled should be presented by subject in the data listings.

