**MC2-01-C6_STATISTICAL ANALYSIS PLAN_Final 3.0_07 September 2020**

Table 14.3.1.9.2 Incidence of Treatment-emergent Adverse Events Leading to Withdrawal up to Week 4

Table 14.3.1.10.1 Incidence of Non-serious treatment-emergent Adverse Events Occurred at a Frequency of $\geq 5\%$

Table 14.3.1.10.2 Incidence of Non-serious treatment-emergent Adverse Events Occurred at a Frequency of $\geq 5\%$ up to Week 4

Table 14.3.1.11 Incidence of Treatment-emergent Adverse Events Related to Cosyntropin

Table 14.3.1.12 Incidence of Treatment-emergent Adverse Events Related to Study Procedures

Table 14.3.2.1 Incidence of Treatment-emergent Adverse Events Leading to Death

Table 14.3.2.2 Incidence of Treatment-emergent Adverse Events Related to the Study Drug and Leading to Death

Table 14.3.4.1.1 Summary of ACTH Challenge Test

Table 14.3.4.1.2 Incidence of HPA Axis Suppression

Table 14.3.4.2.1 Summary of Calcium Metabolism Evaluation

Table 14.3.4.3.1 Summary of Hematology Parameters

Table 14.3.4.3.2 Summary of Blood Chemistry Parameters

Table 14.3.4.3.3 Summary of Morning Urine Assessment Parameters

Table 14.3.4.4.1 Hematology Shifts from Baseline

Table 14.3.4.4.2 Blood Chemistry Shifts from Baseline

Table 14.3.4.4.3 Morning Urine Assessment Shifts from Baseline

Table 14.3.4.5.1 Incidence of Hematology Assessments Outside of Normal Range

Table 14.3.4.5.2 Incidence of Blood Chemistry Assessments Outside of Normal Range

Table 14.3.4.5.3 Incidence of Morning Urine Assessments Outside of Normal Range

Table 14.3.4.6.1 Summary of Local Skin Reactions Assessment

Table 14.3.4.6.2 Local Skin Reactions Assessment Shifts from Baseline

Table 14.3.4.6.3 Summary of LSR Sum Score

Table 14.3.4.7.1 Summary of Vital Signs

Table 14.3.4.7.2 Incidence of Vital Signs Assessments Outside of Normal Range

Table 14.3.4.7.3 Incidence of Notably Abnormal Vital Signs Assessments

Table 14.3.4.8 Summary of Physical Parameters

Table 14.3.4.9 Summary of Physical Examination

Table 14.3.4.10.1 Summary of Electrocardiogram

Table 14.3.4.10.2 Incidence of Abnormal ECG Assessments

Table 14.3.4.10.3 Incidence of Notably Abnormal ECG Assessments

Table 14.4.1.1 Summary of PGA

Table 14.4.1.2 Summary of Treatment Success

Table 14.4.1.3 PGA Shifts from Baseline

Table 14.4.2.1 Summary of Body Surface Area Involvement

Table 14.4.3.1 Summary of Psoriasis Treatment Convenience Scale

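### The cosyntropin- and procedure-related AE tables use the cream's treatment-emergent window, so fully dated reactions to the SV2 ACTH challenge appear only in listings

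*SAP*

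**What the plan says.** SAP 9.2 sets the window by the cream: "An AE is treatment-emergent if its date of onset is on or after the date of the first application of the IP". It then limits all tabulation to that window ("Only treatment emergent AEs will be summarized") and fixes the population: "Number (percentage) of subjects and number of AEs will be presented for the Safety population in the following tables". Two of the tables under that rule concern exposures other than the cream. They are listed in SAP 16.1 as "Table 14.3.1.11 Incidence of Treatment-emergent Adverse Events Related to Cosyntropin" and "Table 14.3.1.12 Incidence of Treatment-emergent Adverse Events Related to Study Procedures". Table 14.3.1.1 carries a row for each.

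Protocol 7.6.2 sets the timing of cosyntropin: "The ACTH challenge test will be performed at SV2, Week 4 and Week 8 visits". The visit-window table in SAP Section 7 places SV2 on Days -7 to -4 relative to first application. Collection starts earlier still. Footnote i of SAP Table 1 reads: "AEs are to be collected from the date of signing informed assent/informed consent and first trial-related activity is performed". The AE listing shell (Listing 16.2.7.1, All Enrolled subjects) has fields for relatedness to cosyntropin and to a study procedure.

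**The concern.** The SAP treats cosyntropin and study procedures as separate causes, with their own causality fields and incidence tables, but applies the cream's clock to them. That clock suits the cream. It does not suit an intravenous agent first given days earlier, or procedures that begin at screening. A reaction at SV2 can be recorded and attributed to cosyntropin and still be barred from the table built for that attribution.

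What is at stake is how Tables 14.3.1.11 and 14.3.1.12 can be read. With 7 treated subjects, one subject is 1/7 = 14%. If one of them reacted at SV2 and at no later test, the table would show 0% instead of 14%.

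**Working it through.** The plan states no figure on this point, so there is none to reproduce. The check is a count of exposures inside and outside the window, followed by a sensitivity calculation.

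**Inputs**
- Scheduled challenges per subject: 3, at SV2, Week 4 and Week 8 (Protocol 7.6.2). A fourth, at follow-up, occurs only if suppression is noted at Week 8 and is not counted here.
- Position of SV2: always before first application (SAP Section 7).
- Subjects: 7 treated at the interim (SAP 6.1). SAP Section 2 says this SAP applies to the interim and that a separate SAP would cover any final analysis.
- Per-challenge reaction risk p: not in the documents. It is assumed constant and independent across challenges, with a range of 1% to 30%.

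**Count of doses**
- Scheduled in treated subjects: 7 × 3 = 21.
- Inside the treatment-emergent window (Week 4 and Week 8): 7 × 2 = 14.
- Outside it (SV2): 7 × 1 = 7, or 7/21 = 33%.
- SV2 doses in subjects never dispensed cream are also outside, because SAP 6.2 excludes those subjects from the Safety population. Their number is unknown. Inclusion criterion 7 is judged on the SV2 test, so anyone who fails its post-challenge cortisol limit has already received cosyntropin.

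**Effect on the subject rate, under the assumed p**
- All three challenges: 1 − (1 − p)³.
- As tabulated: 1 − (1 − p)².
- A given subject reacts only at SV2: q = p(1 − p)².
- At least one of 7 does so: 1 − (1 − q)⁷.

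| p | All three | As tabulated | Ratio | At least 1 of 7 reacts only at SV2 |
|---|---|---|---|---|
| 1% | 3.0% | 2.0% | 0.67 | 6.7% |
| 5% | 14.3% | 9.8% | 0.68 | 27.6% |
| 10% | 27.1% | 19.0% | 0.70 | 44.6% |
| 20% | 48.8% | 36.0% | 0.74 | 61.7% |
| 30% | 65.7% | 51.0% | 0.78 | 67.1% |

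The expected number of events tabulated in treated subjects is 2/3 of the total under constant p.

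**Partial dates**
Under SAP Table 2.2, an event with the day missing counts as treatment-emergent if its month and year are not before those of the first dose. With only the year known the comparison is by year, and with the year missing the event always counts. An incompletely dated SV2 reaction in a treated subject can therefore enter the table, while the same reaction with a full date cannot.

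**Procedure table**
The one-third share does not carry over, because procedures have no common unit. By planned maximum blood volume (Protocol 7.6.1), for example, SV2 accounts for 17 of 17 + 8 + 41 + 17 = 83 ml across SV2 and Weeks 2, 4 and 8, which is 20%. No overall size can be given.

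**The case against.** The strongest defence is that nothing is lost or mislabelled. All AEs are listed, those that are not treatment-emergent are identified as such, and Listing 16.2.7.1 includes screen failures. With 7 treated subjects a reader could count SV2 reactions by hand. Both tables are titled treatment-emergent, so they report on-treatment incidence as labelled. Protocol 8.8.3 also summarises treatment-emergent AEs, and cosyntropin is a diagnostic agent rather than the product under evaluation.

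Much of this stands, and it keeps the point minor. It does not make the cream's window suitable for an exposure that starts earlier. The protocol does not exclude other summaries and plans no cosyntropin table, so a wider window contradicts nothing in it.

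A reader might also infer more than the documents support:
- *That every SV2 reaction is left out.* The listings hold them all, and the partial-date rule can admit some to the table.
- *That the tabulated subjects are those who tolerated the first test.* No entry criterion requires tolerance. Inclusion criterion 7 concerns cortisol values, so a subject can react at SV2 and still receive cream.
- *That the rate is always too low.* In treated subjects it equals the all-challenge rate if nobody reacts only at SV2.
- *That the shortfall is 30 of 90 doses at the planned sample size.* That case lies outside this interim-only SAP.

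**Conclusion.** The point holds in a limited form. Tables 14.3.1.11 and 14.3.1.12, and their rows in Table 14.3.1.1, cannot show a fully dated event from SV2 or any event in a subject never dispensed cream. For cosyntropin this removes 7 of the 21 scheduled doses in treated subjects at the interim. The subject rate is understated if anyone reacts only at SV2. Under constant, independent risk between 1% and 30%, it would be about 0.67 to 0.78 of the all-challenge rate in expectation. That range is an assumption, and the documents give no reaction rate. A zero in the table would not mean that no reaction occurred.

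The effect is confined to secondary safety reporting. This is a cheap improvement.

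**What to change.** - **Table 14.3.1.11:** count all cosyntropin-related AEs with onset on or after the first challenge, whatever their treatment-emergent flag. Use subjects who received at least one cosyntropin dose as the denominator, and split the counts into before and after first cream application.
- **Table 14.3.1.12:** add a separate row for procedure-related AEs that start before first application, with subjects who underwent at least one study procedure in that period as the denominator. Using everyone who consented would dilute the rate, because the All Enrolled set in SAP 6.2 includes early screen failures who had few procedures.
- **Table 14.3.1.1:** align the two matching rows and footnote the differing denominators here and in the two tables above.
- **All other AE tables:** keep the treatment-emergent rule.

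The cost is a wording change in SAP 9.2, two table shells, the two rows of Table 14.3.1.1 and footnotes. The data are already collected and listed. SAP Section 2 allows revision before the interim database lock and explanation in the study report for a later deviation. The downside is that these tables will carry different denominators from the rest of the AE output.

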**MC2-01-C6_STATISTICAL ANALYSIS PLAN_Final 3.0_07 September 2020****9.3. *Pregnancies***

eCRF form: “URINE PREGNANCY TEST”, “SERUM PREGNANCY TEST”.

All female subjects will undergo a routine urine pregnancy test at SV1 and V1 (Day 0) and a serum pregnancy test at SV2, Week 4 & Week 8 as specified in the visit schedule (Table 1).

The results of these tests and pregnancies episodes will be reported in the listing.

9.4. *Clinical Laboratory Evaluations*

eCRF form: “LABORATORY ASSESSMENT”, “SERUM CHEMISTRY”, “MORNING URINE ASSESSMENT”, Central laboratory data.

Clinical laboratory data will be summarized by presenting shift tables using extended normal ranges (baseline to most extreme post-baseline value), by presenting summary statistics of raw data and change from baseline values (means, medians, standard deviations (SDs), ranges), and by the flagging of notable values (out of range values) in data listings.

Clinical laboratory evaluations as scheduled in the Table 1 include the following parameters:

- Hematology: hemoglobin, hematocrit, red blood cell (RBC) count, mean corpuscular volume (MCV), white blood cell (WBC) count, including differential count and platelet count.
- Serum biochemistry: cortisol, urea, glucose, creatinine, calcium, albumin, calcium (albumin corrected), sodium, potassium, chloride, phosphate, alkaline phosphatase (ALP), plasma parathyroid hormone (PTH).
- 25-OH Vitamin D, only at SV2
- Morning urine assessment: calcium, phosphate, creatinine, volume, total calcium excretion, total phosphate excretion, total creatinine excretion, urinary calcium:creatinine ratio, urinary phosphate:creatinine ratio.

Week 4: If albumin-corrected serum calcium is above the reference range at Week 4, a repeat test should be performed at Week 6. If the morning urinary calcium:creatinine ratio is above the reference range at Week 4, a repeat test should be performed at Week 6.

Week 8: If the albumin-corrected serum calcium is above the reference range at Week 8, a repeat test is required 14 days (\pm 2 days) after at a follow-up visit. If the urinary calcium:creatinine ratio is above the reference range at Week 8, a repeat test is required at a follow-up visit 14 days (\pm 2 days) after Week 8. If the calcium-creatinine ratio is above the reference range at two consecutive visits during the trial, 24-hour urine collection must be performed.

For laboratory parameters the following tables will be presented according to section 7:

- descriptive statistics of measured values and changes from baseline by visit including highest/lowest post-baseline value;

**MC2-01-C6_STATISTICAL ANALYSIS PLAN_Final 3.0_07 September 2020**

- shift tables based on comparison with normal range (Low/Normal/High) by visit and to highest/lowest post-baseline value;
- frequency tables for Out of range: Normal/Out of range (Low/High) for laboratory parameters by visit.

Clinical laboratory values will be reported as complete listings of individual subject data.

A separate listing will be prepared for all clinically significant abnormal results.

9.5. Other Safety Measures

HPA-axis suppression

The primary outcome variable for HPA axis is serum cortisol level of less than 18 µg/dL (500 nmol/L) at 30 minutes after ACTH challenge test (at Week 4 and Week 8).

The number and proportion of subjects with HPA-axis suppression at Week 4 and Week 8 will be summarised using frequency counts, percentages and exact 95% CI. Percentage will be calculated based on number of valid measurements (number of subjects for whom ACTH challenge test was performed) at each post-baseline visit. Number and proportion (95% CI) of subjects for whom HPA-axis suppression was noted at least once during the study will be presented. For Week 8, number and proportion of subjects with HPA-axis suppression will be additionally presented by HPA suppression status at Week 4.

Serum cortisol level at each time point (pre- and post- ACTH challenge test) will be summarized in tables with standard descriptive statistics for continuous variables and 95% CI for the means.

Calcium metabolism

Changes from Baseline to Week 4 and Week 8 in:

- Albumin-corrected serum calcium;
- Ratio of urinary calcium to creatinine*.

*Spot analysis, second morning urine sample

Descriptive statistics for measured parameters as well as changes from baseline will be presented by visit of assessment as scheduled in the Table 1.

Vital signs

eCRF form: “VITAL SIGNS”.

